#### 4.2 Treatment Administration

Table 4-2-1: Premedications *			
Premedication	Dose	Route	Schedule
Diphenhydramine*	25 mg	Treating investigator discretion / Institutional standards	Administer at least 30 minutes prior to the sEphB4-HSA infusion
Acetaminophen*	650 mg	PO	Administer at least 30 minutes prior to the sEphB4-HSA infusion

\* Refer to Section 4.4.3 for (1) changes to the pre-medication regimen for patients who experience infusion reactions and (2) management of infusion reactions.

Table 4-2-2: Treatment Administration Summary					
Agent	Dose	Route	Schedule	Cycle Length	Supportive Therapies*
sEphB4-HSA	1000mg	IV over 60 minutes ( $\pm 15$ min)	Cycles 1-6: Day 1 of each cycle (14 days) Cycle 7+: Day 1 of each cycle (21 days)	Cycle 1-6: 14 days Cycle 7+: (21 days)	Antiemetics Additional medications for prophylaxis and supportive care can be administered as clinically indicated per Institutional standards.

\* Refer to Section 4.4.3 for the management of infusion reactions.

NU Study Number: NU 18U10

sEphB4-HSA will be administered intravenously. The dose of sEphB4-HSA will be 1000mg intravenously over 60 minutes ( $\pm 15$  min) on day 1 of a 14-day cycle. Beginning at Cycle 7, cycle length will be 21 days and patients will return for treatment on Day 1 of each cycle. Premedications include diphenhydramine and acetaminophen as described above in Table 4-2-1. Additional medications for prophylaxis and supportive care can be administered as clinically indicated per institutional protocol.

#### 4.3 Toxicity Management & Dose Delays/Modifications

Any patient who receives at least one dose of study therapy will be evaluable for toxicity endpoints. Each patient will be assessed for the development of toxicity according to the timeframe referenced in the Schedule of Events table (section 5). Toxicity will be assessed according to CTCAE v5.0.

- In order to start a new cycle of therapy a patient must have platelets  $\geq$  100,000, ANC  $\geq$  1,000, and resolution of all treatment-related toxicity (except alopecia) to Grade 2 or less or to baseline when baseline was more than Grade 2.
- A dose can be delayed for up to 7 days for resolution of toxicity. The subsequent doses will be delayed so as not to shorten the dosing interval.
- If the dose cannot be given within 7 days of scheduled time it should be omitted. Patients who miss 3 consecutive doses will be removed from the study.
- Patients will be withdrawn from the study if they fail to recover to CTCAE 5.0  $\leq$  1 or baseline from a drug-related toxicity (except alopecia)  $\leq$  4 weeks.
- Patients can have a maximum of 2 dose reductions for drug-related toxicity beyond which they will be removed from the study. Dose reduction should follow the dose levels displayed in the table below. Re-escalation is not permitted.

Dose modifications

Dose Level	Dose of sEphB4-HSA
Starting Dose	1000mg IV over 60 min every 2 weeks
-1	750 mg IV over 60 min every 2 weeks
-2	500 mg IV over 60 min every 2 weeks

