## 4 TREATMENT PLAN

### 4.1 Overview

This study plans to enroll two successive cohorts by a Simon two-stage design of 15 and 10 evaluable patients, for possible total of 25 evaluable patients with progressive mCRPC after treatment with at least one first-line therapy for metastatic castration-resistant prostate cancer including new AR targeted therapy (i.e. abiraterone, enzalutamide or similar agents) or chemotherapy (docetaxel or cabazitaxel or noavel taxane). The second cohort will be recruited if the first cohort shows a signal of activity and no signs of unexpected toxicity; see section 6.1 for definitions.

- Patients will receive sEphB4-HSA 1000mg IV ( $60 \pm 15$  min infusion) on day 1 in a 14-day cycle along with continuation of androgen deprivation therapy. Assessment of response to therapy with PSA will be every odd cycle (every 28 days). Imaging will occur at baseline and 2 months after starting therapy; thereafter, imaging will be conducted every 3 months. After 1 year, imaging can be done every 4 months for patients with stable disease or better. Scans may also be conducted at any time, if clinically indicated. Beginning at Cycle 7, cycle length will be 21 days and patients will return for treatment on Day 1 of each cycle.

*Note: patients will receive ADT per treating physician's choice (LHRH agonist/antagonist or orchiectomy) as standard therapy.*

NU Study Number: NU 18U10

- Cell Free DNA (cfDNA) will be collected at baseline and on Day 1 of cycle 5, and at disease progression or end of treatment for molecular analysis. We will collect serum for cytokine panel analysis (TNFa, IL1beta, IL2, 4, 5, 6, 8, 10, 12, 13) at baseline Day 1 of cycle 5 prior to drug infusion and at disease progression or end of treatment.

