## NU Study Number: NU 18U10

vomiting, and diarrhea		drug will require immediate dose interruption. Treatment will be withheld until toxicities have resolved to Grade 1 or baseline. After resolution of the toxicity, a one dose level reduction will be initiated.
AST/ALT	Grade 3	Grade 3 AST and/or ALT that does not represent at least a two grade increase from baseline – hold therapy, recheck weekly. If AST and ALT return to baseline grade within 7 days, retreat at same dose level. If AST and ALT do not return to baseline within 7 days, treatment should be restarted once AST and ALT have returned to baseline and dose should be reduced by one level.  Grade 3 AST and/or ALT that represents at least a two grade increase from baseline or $AST/ALT \geq 10 \times UNL$ –hold therapy, recheck weekly, initiate retreatment when resolved to baseline with one dose level reduction.
	Grade 4	Grade 4 AST and/or ALT– hold therapy, recheck weekly, initiate retreatment when resolved to baseline with a one level dose reduction.  Any grade AST or ALT that represents a doubling from baseline AND that is concurrent with a doubling of the total bilirubin- hold therapy, recheck weekly, initiate retreatment when resolved to baseline grade or grade 1 with one level dose reduction.
	Grade 2	Patients with grade 2 hypertension as evidenced by two or more different measurements that are at least one our apart should be initiated on antihypertensive therapy per the treating physician. BP should be rechecked in one week after initiation of antihypertensive therapy; if SBP is still $>150$ and/or DBP is $> 100$ , physician should increase the dose of the antihypertensive or add a second antihypertensive drug as indicated.
Hypertension 	Grade 3	First occurrence, patients may continue on treatment while their antihypertensive therapy is optimized. A second occurrence of grade 3 hypertension despite antihypertensive therapy would require holding treatment with sEphB4-HSA until hypertension returns to $\leq$ grade 2 at which point treatment can be resumed with one dose reduction.
	Grade 4	Withhold study drug. Optimal management with intensive IV support in ICU.
Platelets	Grade 3/4	Hold therapy, recheck weekly, initiate retreatment when resolved to Grade 1 or less and restart treatment with a one level dose reduction.

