8. Permission to obtain archival tissue samples of primary lesion and metastatic lesion sites will be obtained at baseline. The samples themselves will be collected only if available and only when requested by the Principal Investigator or Principal Investigator's designee; they may be collected at any time during the study, per PI request. Refer to the lab manual for details.
9. If there is concern about transformation to small cell cancer histology then a standard of care biopsy may be appropriate given that this is an exclusion criteria for this trial.
10. If tumor tissue is biopsied or resected as part of standard medical care or assessment from the time of study enrollment until progression then archival tissue from this biopsy/resection may be used for assay of the markers defined within the protocol to document molecular pathway characteristics and immune cell infiltration at that point to correlate with whether the cancer is responding, stable or progressing.
11. Patients will receive sEphB4-HSA 1000mg IV (60min infusion) on day 1 of each cycle along with continuation of androgen deprivation therapy. Refer to Table 4-2-1 for required premedication regimens.
12. Imaging must be completed and reviewed within 6 days (whenever feasible) prior to receiving treatment.
13. **Please see Table Below.** Beginning at Cycle 7, cycle length will be 21 days and patients will return for treatment on Day 1 of each cycle.
14. Patients will return for an End of Treatment (EOT) visit 30 ( $\pm 3$ ) days of the last dose of study treatment or prior to start of new treatment.
15. If off treatment for reasons other than disease progression, patients will be followed every 6 months, until objective progression or patient starts alternative therapy for a maximum of 1 year.
16. If patient has had molecular testing (i.e., NGS testing, genetic testing, genomic testing, etc.) performed as standard of care prior to study entry or at any time during study participation, collect a copy of the results report for correlative analyses. Refer to Section 9 for details.
17. Screening/baseline assessments are to be conducted within 1 month prior to registration unless otherwise indicated.

## Study Calendar Beginning at Cycle 7

Time Period	On Treatment (1 Cycle = 21 Days)						Off Treatment	
	Cycle 7	Cycle 8	Cycle 9	Cycle 10	Cycle 11	Cycle 12+	End of Treatment 	Follow-up 
	Week 13 Day 1	Week 16 Day 1	Week 19 Day 1	Week 22 Day 1	Week 25 Day 1	Week 28 Day 1		

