**8.1.5 Protocol dose specifics**

sEphB4-HSA will be given as 1000mg IV infusion over 60 minutes ( $\pm 15$  minutes) every 2 weeks on day 1 ( $\pm 3$ ) of each cycle during Cycles 1-6 (1 cycle =14 days). Beginning at Cycle 7, patients will receive sEphB4-HSA every 3 weeks on Day 1 of each cycle (1 cycle = 21 days).

Refer to Table 4-2-1 for required premedication regimens.

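### The Section 4.3 dose-level table prints every level as every 2 weeks, but dosing is every 3 weeks from Cycle 7, so the interval for a reduced-dose patient from Cycle 7 is not defined (375 or 250 mg per week at level -1)

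*Combined protocol and SAP*

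**What the plan says.** Section 4.3 allows at most two dose reductions for drug-related toxicity, bars re-escalation, and states: "Dose reduction should follow the dose levels displayed in the table below". The table has three rows, each a dose with an interval. The starting row is 1000 mg with a two-week interval, level -1 is "750 mg IV over 60 min every 2 weeks", and level -2 is "500 mg IV over 60 min every 2 weeks". No row or note covers the 21-day cycles.

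Section 4.3.1 orders reductions by level and does not restrict them to particular cycles. For general grade 3/4 non-hematologic toxicity, for example: "After resolution of the toxicity, a one dose level reduction will be initiated". Its anemia entry sends patients to levels -1 and -2 by name, and those levels are defined only in the Section 4.3 table.

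The schedule sections say something different about the interval:

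- Section 4.1: "Beginning at Cycle 7, cycle length will be 21 days and patients will return for treatment on Day 1 of each cycle".
- Section 4.2, Table 4-2-2 and the text below it: 14-day cycles for Cycles 1-6, then 21-day cycles.
- Section 5: footnote 13 and a separate calendar with visits at Weeks 13, 16, 19, 22, 25 and 28 for Cycles 7 to 12+.
- Section 8.1.5: "Beginning at Cycle 7, patients will receive sEphB4-HSA every 3 weeks on Day 1 of each cycle".

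None of these makes an exception for a patient at a reduced level.

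**The concern.** The interval is part of how each dose level is defined, and the table is the instruction that reductions are to follow. From Cycle 7 the documents therefore give two intervals for the same patient. This affects a patient reduced in Cycles 1-6 who reaches Cycle 7, and a patient first reduced at Cycle 7 or later. Two of the three sites could each point to protocol text and treat such a patient differently. Section 11.6 requires the study to be run exactly as the approved protocol describes, so it is also unclear which practice would be a deviation.

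This is an operative rule for managing toxicity. Under one combination of the passages, a step meant to lower the dose raises the weekly amount. A smaller consequence is that the Section 10.2 summaries of adverse events, time to PSA progression and rPFS could pool reduced-dose patients treated at different weekly doses without showing it.

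**Working it through.** The documents state no weekly dose, so there is no planned figure to reproduce.

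**Inputs.** Doses of 1000, 750 and 500 mg (Section 4.3 table). Interval of 2 weeks (Section 4.3 table; Cycles 1-6 elsewhere) or 3 weeks (Sections 4.1, 4.2, 5 and 8.1.5, from Cycle 7).

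**Formula.** Weekly dose = dose per infusion / interval in weeks. Percent change = new weekly dose / old weekly dose - 1.

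| Regimen | mg per week | Against 1000 mg every 3 weeks | Against 1000 mg every 2 weeks |
|---|---|---|---|
| 1000 mg every 2 weeks | 1000/2 = 500 | +50% | reference |
| 1000 mg every 3 weeks | 1000/3 = 333.3 | reference | -33.3% |
| 750 mg every 2 weeks | 750/2 = 375 | +12.5% | -25% |
| 750 mg every 3 weeks | 750/3 = 250 | -25% | -50% |
| 500 mg every 2 weeks | 500/2 = 250 | -25% | -50% |
| 500 mg every 3 weeks | 500/3 = 166.7 | -50% | -66.7% |

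**Spread between the two readings.** Level -1: 375/250 = 1.5. Level -2: 250/166.7 = 1.5.

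**When a rise can occur.** Section 5 puts Cycle 6 Day 1 at Week 11, Cycle 7 Day 1 at Week 13 and Cycle 8 Day 1 at Week 16. The first 21-day gap is therefore between Cycles 7 and 8. For a first reduction to level -1 there are three cases:

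1. *Reduced in Cycles 1-6.* The patient is on 375 mg per week on reaching Cycle 7. The printed interval keeps 375, and the 21-day cycle gives 250. There is no rise in this patient's own rate, although 375 exceeds the 333.3 that a never-reduced patient receives from Cycle 7.
2. *Reduced dose first given at Cycle 7 Day 1.* The preceding rate is 500. The printed interval gives 375 (-25%). The 21-day cycle gives 250 (-50%, part of it from the scheduled change of interval).
3. *Reduced dose first given at Cycle 8 or later.* The preceding rate is 333.3. The printed interval gives 375, and 375/333.3 = 1.125, a 12.5% rise. The 21-day cycle gives 250 (-25%).

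Over six weeks, case 3 compares 2 x 1000 = 2000 mg before reduction with 3 x 750 = 2250 mg on the printed interval or 2 x 750 = 1500 mg on the 21-day cycle.

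**Effect on the design.** The Simon rule in Section 10.1 (15 patients, continue with 2 or more responses; 25 patients, success with 6 or more) uses response counts only. Recomputed exactly, it gives the printed early-stopping probability 0.549, alpha 0.033, beta 0.198 and average sample size 19.51. No dose or interval enters it.

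**The case against.** The strongest reply is that the table fixes milligrams and the schedule sections fix the interval. Much supports it. The starting row also carries the two-week interval, although unreduced patients plainly move to three weeks, which suggests that the printed interval simply describes Cycles 1-6. Section 8.1.5 is unconditional. The calendar from Cycle 7 has only 21-day columns, so a two-weekly patient would need visits it does not contain. Section 4.3.1 speaks of levels and never of shortening an interval. This makes the milligrams-only reading plausible, but no sentence states it. The Section 4.3 sentence against shortening the dosing interval concerns doses that follow a delay, so it does not settle what happens after a reduction.

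The reply is also right that the 12.5% rise needs a mixed reading, with the unreduced interval from Section 8.1.5 and the reduced interval from the table. Using the table for both (500 to 375) or the 21-day cycle for both (333.3 to 250) gives a 25% cut.

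A reader might infer that every reduction from Cycle 7 onward raises the weekly dose. The documents do not support that: cases 1 and 2 show no rise. A reader might also infer that a patient in case 3 is exposed beyond anything given earlier in the trial. That is not so either, because 375 mg per week is 25% below the Cycle 1-6 rate. Finally, an interval difference by itself says little about the Section 10.2 outcomes, since every patient who reaches Cycle 8 changes interval by design.

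**Conclusion.** The contradiction stands: the dose-level table and the schedule sections give different intervals for a reduced-dose patient from Cycle 7, and nothing in the documents says which governs. Its size is a 1.5-fold difference in weekly dose at either reduced level (375 or 250 mg; 250 or 167 mg). The rise from 333 to 375 mg per week (+12.5%) is conditional. It applies only if the printed interval is given to a patient who was on 1000 mg every 3 weeks, with the reduced dose first given at Cycle 8 or later.

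The number of patients concerned is not in the documents. The only duration figure is the phase I median of 2 cycles (range 1-19) in Section 1.5, from a different population and with no cycle length stated. It suggests that few patients may reach Cycle 7, and those also reduced would be fewer still.

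It would be wrong to conclude that the primary analysis is compromised: the sample size, error rates, power and decision rule are unaffected, and Section 10.1 needs no edit. The point is worth acting on because the ambiguity lies in a toxicity rule and is cheap to remove.

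**What to change.** Reconcile the Section 4.3 table with Sections 4.1, 4.2, 5 and 8.1.5. The text should state which interval applies from Cycle 7 to a patient at a reduced level, separately for reductions made in Cycles 1-6 and for those made at Cycle 7 or later. The calendar from Cycle 7 should agree with whatever is stated. This review does not say which passage is right and proposes no dose or interval.

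For any patient already treated at a reduced level from Cycle 7, list the dose and interval actually given, so that the Section 10.2 summaries can be read with that in view.

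The cost is a table note or a sentence in an amendment, a notice to the three sites, and a look-back at dosing records. The sample size and decision rule do not change.

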##### 4.3.1 Dose modifications for sEphB4-HSA treatment related toxicity

Toxicity	Grade	sEphB4-HSA
Non-hematologic toxicities including nausea, vomiting , and diarrhea	Grade 1/2	If patients develop intolerable Grade 1 or Grade 2 toxicities (per patient) then they can undergo a dose reduction. For Grade 3/4 toxicities despite optimal medical therapy, hold sEphB4-HSA until equal or under Grade 1. Resume at one dose level reduction.  No routine prophylactic anti-emetic treatment is required at the start of study treatment, however, patients should receive appropriate anti-emetic treatment at the first onset of nausea or vomiting and as required thereafter, in accordance with local treatment practice guidelines
General non-hematologic toxicities excluding nausea,	Grade 3/4	Any patient who experiences Grade 3 or 4 unmanageable non-hematologic toxicity (other than alopecia) at least possibly related to the study

## NU Study Number: NU 18U10

vomiting, and diarrhea		drug will require immediate dose interruption. Treatment will be withheld until toxicities have resolved to Grade 1 or baseline. After resolution of the toxicity, a one dose level reduction will be initiated.
AST/ALT	Grade 3	Grade 3 AST and/or ALT that does not represent at least a two grade increase from baseline – hold therapy, recheck weekly. If AST and ALT return to baseline grade within 7 days, retreat at same dose level. If AST and ALT do not return to baseline within 7 days, treatment should be restarted once AST and ALT have returned to baseline and dose should be reduced by one level.  Grade 3 AST and/or ALT that represents at least a two grade increase from baseline or $AST/ALT \geq 10 \times UNL$ –hold therapy, recheck weekly, initiate retreatment when resolved to baseline with one dose level reduction.
	Grade 4	Grade 4 AST and/or ALT– hold therapy, recheck weekly, initiate retreatment when resolved to baseline with a one level dose reduction.  Any grade AST or ALT that represents a doubling from baseline AND that is concurrent with a doubling of the total bilirubin- hold therapy, recheck weekly, initiate retreatment when resolved to baseline grade or grade 1 with one level dose reduction.
	Grade 2	Patients with grade 2 hypertension as evidenced by two or more different measurements that are at least one our apart should be initiated on antihypertensive therapy per the treating physician. BP should be rechecked in one week after initiation of antihypertensive therapy; if SBP is still $>150$ and/or DBP is $> 100$ , physician should increase the dose of the antihypertensive or add a second antihypertensive drug as indicated.
Hypertension 	Grade 3	First occurrence, patients may continue on treatment while their antihypertensive therapy is optimized. A second occurrence of grade 3 hypertension despite antihypertensive therapy would require holding treatment with sEphB4-HSA until hypertension returns to $\leq$ grade 2 at which point treatment can be resumed with one dose reduction.
	Grade 4	Withhold study drug. Optimal management with intensive IV support in ICU.
Platelets	Grade 3/4	Hold therapy, recheck weekly, initiate retreatment when resolved to Grade 1 or less and restart treatment with a one level dose reduction.
Neutropenia	Neutropenic fever or Grade 4 neutropenia	Hold therapy, recheck weekly, initiate retreatment when resolved to Grade 1 or less and restart treatment with a one level dose reduction.
Anemia	Grade 1 or Grade 2 (Hemoglobin (Hb) $> 8$ g/dl)	Investigate and manage as deemed appropriate by the investigator with or without interruption of study drug or change in dose, taking into account previous history of anemia. Common treatable causes of anemia (e.g., iron, vitamin B12 or folate deficiencies and hypothyroidism) should be excluded. In some cases management of anemia

NU Study Number: NU 18U10

		may require blood transfusions.
	Grade 3 (Hb < 8g/dl) or worse	
Study treatment should be interrupted for up to maximum of 4 weeks to allow for bone marrow recovery and the patient should be managed appropriately. Study treatment can be restarted at the reduced dose level -1 if Hb has recovered to > 10 g/dl. Any subsequently required anemia related interruptions, considered likely to be dose related, or coexistent with newly developed neutropenia, and or thrombocytopenia, will require a further study treatment dose reduction to level -2.
 
If a patient has been treated for anemia with multiple blood transfusions without study treatment interruptions and becomes blood transfusion dependent as judged by investigator, study treatment should be permanently discontinued.

1. All patients will be educated about the hypertension side effect and instructed to contact the study team if their blood pressure remains under poor control between visits. The patients may be asked to keep a blood pressure log as per treating physician discretion.

*NOTE: Stopping or reducing the dose of study drug can cause a decrease in BP. The treating physician should monitor the patient for hypotension and adjust the number and dose of antihypertensive medication(s) accordingly.*

If the patient experiences a grade 4 allergic or hypersensitivity reaction the drug should be permanently discontinued.

AR targeted therapy will continue per standard of care regardless of sEphB4-HSA toxicity.

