#### 4.3.2 Toxicities that require discontinuation from protocol therapy

Protocol therapy should be discontinued if a patient experiences:

- Any CTC Grade 4 toxicity with the exception of:
  - CTC Grade 4 neutropenia of 5 days or fewer duration
  - CTC Grade 4 nausea/vomiting or diarrhea that resolves to Grade 3 or less within 72 hours despite optimal supportive care.
  - CTC Grade 4 laboratory abnormalities that can be readily corrected within 72 hours and do not result in hospitalization.
- CTC Grade 3 thrombocytopenia with hemorrhage
- CTC Grade 3 febrile neutropenia
- Hy's Law (AST or ALT >3x ULN with concomitant serum bilirubin >2x ULN and no alternate etiology)

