For Grade 3 or Grade 4 symptoms: (grade 3: Symptomatic bronchospasm, with or without urticarial, requiring parenteral medications; allergy related edema/angioedema, hypotension OR grade 4: Anaphylaxis as defined as a life-threatening event characterized by the rapid onset of airway obstruction including bronchospasm, stridor, hoarseness, urticarial and/or hypotension): Immediately discontinue infusion of sEphB4-HSA. Begin an i.v. infusion of normal saline, and treat the subject as follows: Recommend bronchodilators, epinephrine 0.3 mg of a 1:1,000 solution for intramuscular administration, or 0.1 to 0.25 mg of a 1:10,000 solution injected slowly for i.v. administration, and/or diphenhydramine 50 mg i.v. with methylprednisolone 100 mg i.v. (or equivalent), as needed. Subject should be monitored until the investigator is comfortable that the symptoms will not recur. sEphB4-HSA will be permanently discontinued. Investigators should follow their institutional guidelines for the treatment of anaphylaxis. Remain at bedside and monitor subject until recovery from symptoms. In the case of late-occurring hypersensitivity symptoms (e.g., appearance of a localized or generalized pruritus within 1 week after treatment), symptomatic treatment may be given (e.g., oral antihistamine, or corticosteroids).

Severe infusion reactions, including fatal reactions, have been observed in mice (but not in monkeys). All clinical sites must have immediate access to emergency medications and equipment and staff trained in CPR in addition to the ability to rapidly transfer patients to an intensive care setting if a patient experiences a severe infusion reaction.

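### A Grade 3 infusion or hypersensitivity reaction judged unmanageable falls under two opposing re-dosing rules (4.3.3 and the general row of 4.3.1), and both pointers to the reaction rules cite a section that does not exist

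*Combined protocol and SAP*

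**What the plan says.** Section 4.3.3 (Management of Infusion Reaction) handles Grade 3 and Grade 4 reactions together. It opens: "For Grade 3 or Grade 4 symptoms: (grade 3: Symptomatic bronchospasm, with or without urticarial, requiring parenteral medications; allergy related edema/angioedema, hypotension", and then gives anaphylaxis as the Grade 4 case. After the emergency measures, the instruction for both grades is: "sEphB4-HSA will be permanently discontinued".

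The table in Section 4.3.1 has a row for general non-hematologic toxicities of Grade 3 or 4. Its label leaves out nausea, vomiting and diarrhea. Its trigger begins: "Any patient who experiences Grade 3 or 4 unmanageable non-hematologic toxicity (other than alopecia) at least possibly related to the study" (the sentence goes on to name the drug and require an immediate interruption). The row continues: "Treatment will be withheld until toxicities have resolved to Grade 1 or baseline". It ends: "After resolution of the toxicity, a one dose level reduction will be initiated". In the dose table of Section 4.3, one level below the starting dose of 1000 mg is "750 mg IV over 60 min every 2 weeks", and the next level is 500 mg.

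One sentence under the 4.3.1 table concerns allergy: "If the patient experiences a grade 4 allergic or hypersensitivity reaction the drug should be permanently discontinued".

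Section 4.3.2 lists toxicities that end protocol therapy. It includes Grade 4 toxicity with three exceptions. The Grade 3 events it names are thrombocytopenia with hemorrhage and "CTC Grade 3 febrile neutropenia". A Grade 3 infusion or hypersensitivity reaction is not on the list.

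The footnotes to Tables 4-2-1 and 4-2-2 in Section 4.2 send the reader to Section 4.4.3 for the handling of infusion reactions. Section 4.4 covers concomitant medications and has no numbered subsections.

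**The concern.** Re-dosing after a serious reaction should have one answer, wherever in the protocol a site looks. Here a clinician who works from the dose-modification table can reach a different answer from one who reads the reaction section. Nothing in 4.3, 4.3.1, 4.3.2 or 4.3.3 says which of the two prevails.

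What is at stake is patient safety: a further dose, at a reduced level, after bronchospasm or angioedema has resolved, although 4.3.3 rules out any further dose. The protocol calls such reactions unlikely and documents no Grade 3 reaction. The question is not purely theoretical, though. The Amendment 5 entry in Appendix V records that one enrolled subject had an infusion reaction, grade not stated, and that premedication was made mandatory as a result. Section 4.3.3 also reports severe and fatal infusion reactions in mice, though not in monkeys.

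**Working it through.** No figure in the plan needs to be reproduced, and no probability can be computed because the documents give no infusion-reaction rate. The check sets the four relevant texts side by side and then reads the doses from the table in 4.3.

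| Text | Grade 3 reaction | Grade 4 reaction |
|---|---|---|
| 4.3.3 | Permanent stop | Permanent stop |
| 4.3.1 general row, if the reaction is judged unmanageable and at least possibly related | Hold, then restart one level lower | Hold, then restart one level lower |
| Sentence under the 4.3.1 table | Silent | Permanent stop |
| 4.3.2 list | Not named | Stop (the exceptions cover neutropenia, gastrointestinal events and correctable laboratory values) |

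**Grade 4.** The general row nominally reaches Grade 4 as well, but three other texts stop the drug, two of them in terms specific to reactions. The practical answer is not in doubt.

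**Grade 3.** Only 4.3.3 stops the drug. The general row restarts it. The other two texts say nothing about Grade 3 reactions, so they neither permit rechallenge nor settle the matter.

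**Whether the row is reached.** A Grade 3 bronchospasm or angioedema is non-hematologic and, during an infusion, at least possibly drug-related. It is not among the carved-out events (nausea, vomiting, diarrhea, alopecia). The remaining condition is that it be unmanageable. With no definition, a reaction that needs parenteral medication could be judged either way.

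**Next dose if the row is reached** (dose levels from 4.3):

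- Patient on 1000 mg: 0 mg under 4.3.3; 750 mg under the row, which is 750/1000 = 0.75 of the starting dose.
- Patient on 750 mg: 0 mg under 4.3.3; 500 mg under the row, which is 500/1000 = 0.50 of the starting dose.
- Patient on 500 mg: no lower level exists, and 4.3 removes patients who would need more than two reductions, so both routes end treatment.

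If the reaction is judged manageable, the row does not apply and only 4.3.3 speaks.

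**Pointers.** Two footnotes in 4.2 refer to the reaction rules, and both (2 of 2) cite 4.4.3. The rules are in 4.3.3. The table of contents lists only two-level headings, so it does not show 4.3.3 either.

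**The case against.** The best case against this point is that the specific rule beats the general one. Section 4.3.3 has its own heading, names the Grade 3 events, and is mandatory about stopping. Appendix V records its reaction instructions as an FDA-requested addition in Amendment 3. The competing row is labelled general and needs an unmanageable toxicity, whereas 4.3.3 describes how to manage these very events. The wrong section number is an obvious slip, because both footnotes name their subject in words and only one section matches.

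Most of this stands. A site that follows 4.3.3 breaks no rule, and the overlap is narrower than a first reading suggests. What remains is that the precedence is unwritten, the key word is undefined, and the references meant to guide sites fail. The Table 4-2-1 footnote also covers changes to premedication after a reaction, so its error reaches beyond Grade 3.

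Three stronger readings are tempting, and the documents do not support them.

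- A reader might infer from the Grade 4 sentence under the 4.3.1 table that rechallenge after Grade 3 is allowed. The sentence is silent on Grade 3, and silence is not permission.
- A reader might infer the same from the 4.3.2 list. That list is not exhaustive: other stopping rules sit in 4.3, 4.3.1 and 4.5.
- A reader might infer that sites may waive the permanent stop, because 4.3.3 introduces its treatment recommendations as open to local modification. That remark most naturally concerns acute care of the reaction and need not reach the stop.

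**Conclusion.** The point holds as a narrow inconsistency. For a Grade 3 infusion or hypersensitivity reaction that a clinician judges unmanageable and at least possibly drug-related, one stated rule bars any further dose and another restarts treatment at 750 mg or 500 mg. The dose contrast exists only when the general row is triggered. It is a difference between dosing instructions and does not measure risk. Separately, the 4.3.1 allergy sentence uses a different grade threshold from 4.3.3, and both cross-references in 4.2 are wrong whatever view is taken of the overlap.

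The conclusion rests on the current text and on one reading: that *unmanageable*, being undefined, can cover a Grade 3 reaction. It does not claim that the protocol as a whole permits rechallenge or that any patient has been re-dosed after such a reaction. It is a minor safety harmonisation that should be made. The PSA response endpoint, the Simon two-stage boundaries and the sample size are unaffected.

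**What to change.** Make 4.3.3 the governing rule through three edits:

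1. In the general Grade 3/4 non-hematologic row of 4.3.1, exclude infusion and hypersensitivity reactions by name and add *see 4.3.3*.
2. In the sentence under the 4.3.1 table, change the event to *Grade 3 or 4 allergic, hypersensitivity or infusion reaction*, so that its threshold matches 4.3.3.
3. In the footnotes to Tables 4-2-1 and 4-2-2, change 4.4.3 to 4.3.3.

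Two additions are optional: name the same event in the 4.3.2 list, and state in 4.3.3 that the permanent stop is not open to local modification.

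The cost is protocol wording in an amendment. There is no change to assessments, sample size or analysis, and no patient loses an option that 4.3.3 leaves open.
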